4.5.2 Pharmacokinetic (Secondary)

N/A

4.6 Analysis of Safety

All safety data will be reported for the Safety Population as per actual product received. The safety profile of the study products will be assessed with respect to AEs in skin health study.

4.6.1 Adverse Events and Serious Adverse Events

All AEs will be reviewed by the Clinical Research Scientist or Designee prior to database lock and will be coded to a System Organ Class (SOC) and Preferred Term (PT) using the Medical Dictionary for Regulatory Activities (MedDRA).

AEs will be classified as skin and non-skin on the AE page of Electronic Case Report Form (eCRF).

Treatment emergent adverse events (TEAEs) are defined as new AEs that occur on or after the start date of first study product application (if this date is missing a suitable alternative will be used e.g., date of randomization). AEs with an onset date/time prior to the first study product application will be considered as non-treatment emergent.

The following summary tables and listings will be presented by study product and overall:

- Table of TEAEs by SOC and PT ([Table 14.3.1.1](#)).
- Table of TEAEs by Skin/Non-Skin and PT ([Table 14.3.1.2](#)).
- Table of treatment-related TEAEs by SOC and PT ([Table 14.3.1.3](#)).
- Table of treatment-related TEAEs by Skin/Non-Skin and PT ([Table 14.3.1.4](#)).
- Table of treatment-emergent serious adverse events (SAEs) by SOC and PT ([Table 14.3.1.5](#)) [only produced if there are more than 5 SAEs].
- Table of TEAEs by SOC, PT, and severity ([Table 14.3.1.6](#)).
- Table of treatment-related TEAEs by SOC, PT and severity ([Table 14.3.1.7](#)).
- Listing of all AEs ([Listing 16.2.7.1](#) for all randomized subjects; [Listing 16.2.7.2](#) for non-randomized subjects).
- Listing of deaths ([Listing 14.3.2.1](#)).
- Listing of non-fatal SAEs ([Listing 14.3.2.2](#)).
- Listing of TEAEs leading to study or product discontinuation ([Listing 14.3.2.3](#)).
- Listing of TEAEs classified as Skin ([Listing 14.3.2.4](#)).

In the event that there is nothing to report, a null table or listing will be produced.

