## Study Products

The 3 test products are developmental cosmetic moisturizers (a serum, lotion and cream), intended to be used topically by healthy individuals with dry facial skin. A fourth reference product will be used as a negative control; saline solution.

A controlled quantity (0.02 mL/cm^2) of each of the study products will be applied to a cell contained within an adhesive semi-occlusive patch system. The number of cells available in the patch system will be 6, of which 4 will be used for the products and 2 will be left blank. Each of the study products will be dispensed into 4 adjacent cells, per the randomization schedule. Three cells will be used for the test products (serum, lotion and cream) and a fourth for the negative control (saline solution). No other products will be applied to subjects enrolled in this study.

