### Notes:

- Visit 1 and Visit 2 could occur on the same day but Visit 2 must be within 14 days of Visit 1.
- A 'patch' contains individual cells, each of the test products and the saline solution (reference product) will be applied into separate single cells. The order of application of the products into the cells will be randomized for each subject. The same sequence within each subject will be used throughout the induction phase. But the sequence will change for each subject for the challenge phase.
- Subjects should avoid missing the first day of application during the Induction Phase, or the day of application during the Challenge Phase.
- Subjects should avoid missing 2 or more consecutive visits or more than 2 alternate visits.

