### 10.5.2 Assessment of Causality

The causality assessment is one of the criteria used when determining regulatory reporting requirements. For each AE (serious and non-serious), the investigator (or medically qualified designee) **must** provide an assessment of causality on the AE CRF page and the SAE form (subject to the classification of the AE). The investigator will also document in the medical notes that he/she has reviewed the AE and assessed causality, where applicable.

A “reasonable possibility” of a relationship conveys that there are facts, evidence, and/or arguments to suggest a causal relationship, rather than a relationship cannot be ruled out. Generally, the facts (evidence) or arguments to suggest a causal relationship should be provided.

The investigator will use clinical judgment to determine the relationship and will also consult the Investigator Brochure (IB), Safety Statement and/or Product Information, for marketed products, in the determination of his/her assessment. Alternative causes, such as underlying disease(s), concomitant therapy, other risk factors, and the temporal relationship of the event to the study product will be considered and investigated.

For each AE/SAE, the investigator must document in the medical notes that he/she has reviewed the AE/SAE and has provided an assessment of causality.

The investigator’s assessment of causality must be provided for all AEs (serious and non-serious); the investigator must record the causal relationship in the CRF, as appropriate, and report such an assessment in accordance with the SAE reporting requirements if applicable.

There may be situations when an SAE has occurred, and the investigator has minimal information to include in the initial report to GSK. **However, it is very important that the investigator always make an assessment of causality for every event prior to the initial transmission of the SAE data to GSK CH.** The investigator may change his/her opinion of causality in light of follow-up information and send an SAE follow-up report with the updated causality assessment.

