#### **12.2.7 Safety Analysis(es)**

Safety analyses will be performed according to the treatment that the subject received, and Adverse events will be coded using the Medical Dictionary for Regulatory Activities (MedDRA).

AEs will be regarded as treatment emergent if they occur on or after the first treatment application.

Treatment Emergent Adverse Events by System Organ Class (SOC) and Preferred Term (PT), Treatment Emergent Adverse Events (skin site related/non-skin site related), treatment-related AEs (skin site related/non-skin site related), will be summarized overall and by treatment group.

Deaths, Non-fatal Serious Adverse Events, Treatment Emergent Adverse Events leading to study or drug discontinuation will be listed.

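### AE displays are laid out by study product although every subject wears all four products at once, so the product columns cannot be interpreted for AEs not located at a patch cell

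*SAP*

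**What the plan says.** - **Exposure.** Protocol section 1 (Study Products) describes one patch per subject: "Three cells will be used for the test products (serum, lotion and cream) and a fourth for the negative control (saline solution". The notes to the protocol's Schedule of Activities say what is randomized: "The order of application of the products into the cells will be randomized for each subject". Randomization decides where each product sits, not which product a subject receives.
- **Layout of AE displays.** SAP 4.6.1: "The following summary tables and listings will be presented by study product and overall". The list that follows covers the TEAE, treatment-related, severity and SAE tables and the listings, including deaths. Protocol 12.2.7 likewise says that AEs "will be summarized overall and by treatment group".
- **Assignment rule.** The only one given is in SAP 4.6: "All safety data will be reported for the Safety Population as per actual product received".
- **Location of the AE.** Protocol 12.2.7 plans summaries of "Treatment Emergent Adverse Events (skin site related/non-skin site related". SAP 4.6.1 says instead: "AEs will be classified as skin and non-skin on the AE page of Electronic Case Report Form (eCRF". Tables 14.3.1.2 and 14.3.1.4 follow the Skin/Non-Skin split.
- **Causality.** Protocol 10.5.2 has the investigator judge each AE against the study product in the singular ("the temporal relationship of the event to the study product will be considered and investigated"). It describes no separate judgement for each of the four products.

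**The concern.** By-product AE columns suit a parallel-group trial, where each subject has one product. Here each subject has four at once, so there are no treatment groups for an event that arises away from the cells. The text gives no rule for linking such an event to a product.

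This affects much of what the AE tables can contain. Under protocol 4.1, 9.2.1 and 10.1, patch-area reactions that the ICDRG scale fully describes are not recorded as AEs, and neither are reactions to the patch or adhesive. The AEs that can belong to one product are therefore the unusual patch-area reactions that fall outside the scale. The rest, such as infections, headaches or a rash elsewhere, cannot be attributed to one product.

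At stake is how the side-by-side columns are read. The protocol gives saline the role of a reference for putting test-product outcomes in context. Matching columns invite the reading that the products are no worse than saline, and non-matching ones invite the reading that they differ. For events away from the cells, neither reading would rest on data.

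**Working it through.** **Figures in the plan.** The documents give no AE rate. Their one statistical figure is the exact 95% interval for 0 of 200 reactions. Its upper limit is 1 − 0.025^(1/200) = 1.83%, which agrees with protocol 12.1 and SAP 1.4. It concerns patch reactions, not AEs.

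**Inputs.**
- N = 280 randomized subjects (protocol 12.1, SAP 1.4), all taken as receiving at least one patch.
- Four products per subject at the same time (protocol section 1, SAP 1.3).
- Share of subjects with an AE not located at a cell: assumed 5%, 10% and 20%.

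**Reading A: the AE is copied to every product received.** With x = 280 × rate, each column shows x, the four columns sum to 4x, and each product-minus-saline difference is x − x = 0.

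**Reading B: each AE is assigned to one product at random.** Each column expects x/4. The range is the 2.5th to 97.5th percentile of one column under an equal four-way multinomial split (200,000 simulated splits).

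| Assumed rate | Overall column (exact 95% CI) | A: each column; sum of four | B: expected per column; range; mean largest-minus-smallest gap |
|---|---|---|---|
| 5% | 14/280 (2.76% to 8.25%) | 14; 56 | 3.5 (1.25%); 1 to 7; 3.8 |
| 10% | 28/280 (6.75% to 14.13%) | 28; 112 | 7 (2.5%); 3 to 12; 5.4 |
| 20% | 56/280 (15.48% to 25.17%) | 56; 224 | 14 (5.0%); 8 to 21; 7.7 |

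Under A the columns are equal whatever the products do. Under B each column understates the rate fourfold and the columns differ by chance alone.

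**Dilution of a cell-specific signal (reading A, 10%).** Suppose six further subjects have an AE at the cell of one test product and none at the saline cell. The any-AE row then reads 34/280 against 28/280 (12.1% v 10.0%, ratio 34/28 = 1.21). Restricted to cell-located AEs it would read 6/280 against 0/280. The absolute difference of six survives, but the contrast is buried in any row that mixes the two kinds of event. A preferred term seen only at cells would still stand out in its own row.

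**Text side by side.**
- The layout sentence in SAP 4.6.1 also governs Listing 16.2.7.2, the AEs of non-randomized subjects. They received no product, so the sentence cannot be applied as written.
- For age, protocol 12.2.3 asks for summaries in each treatment group, but SAP 4.2.1 shows demographics in one overall column. The AE section was not adapted in the same way.
- Table 5-1 has two entries: the definition of prior and concomitant medication, and dropping the by-visit display of the primary endpoint. The change to Skin/Non-Skin is in neither.

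**The case against.** **No comparison is planned.** The primary and secondary objectives name saline as comparator; the safety objective does not. SAP 4.6.1 plans no AE test or interval. This stands, and it limits the harm to how descriptive columns are read.

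**The columns need not be identical.** A reader might infer that the plan forces a zero difference from saline and so biases the safety comparison toward no difference. The documents do not support that. The actual-product rule is an as-treated statement and does not say that an AE is copied to every column. Assignment to one product would give chance differences instead, and the plan defines no AE comparison to bias. A third reading, with events away from the cells shown only in the overall column, is compatible with the layout sentence but is not stated.

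**Deciding material is not visible.** The table shells (SAP Attachment 1) and the full eCRF AE page are not in the text available. The shells may already solve the layout, and the page may already record the cell. It cannot be claimed that either is deficient, only that the SAP text gives no rule.

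**The key outcomes are elsewhere.** Sensitization and irritation are assessed by site and reported by product (SAP 4.4 and 4.5), so they are unaffected. The listing of skin TEAEs (14.3.2.4) together with the randomization listing (16.1.7.1) might allow some reconstruction by hand. That does not mend the summary tables.

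**The layout comes from the protocol.** Protocol 12.2.7 already asks for AE summaries by treatment group. This is correct, and it means the remedy departs from the protocol and must be recorded as a change.

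**Skin may mean skin site related.** Neither term is defined, so the change may be one of wording only. As written, though, Skin covers a rash on the arm as well as one at a cell.

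**Conclusion.** The point holds as a flaw in a stated layout. For AEs not located at a patch cell, the by-product columns carry no product information under either way of filling them. At an assumed 10% rate in 280 subjects, that means 28 in every column or about 7 in each, against a valid overall figure of 28. The pattern is the same at 5% and 20%.

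The consequence is moderate: columns that can be misread as showing the products equal to saline, and dilution of any AE signal specific to one cell. The overall column and the primary and secondary endpoints are sound, and by-product display is right for AEs at an identified cell. The replacement of the site-related split and its absence from Table 5-1 are a smaller but real documentation gap.

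The conclusion rests on simultaneous exposure and the absence of an attribution rule, both in the text. The counts rest on assumed AE rates, and reading B also on equal random assignment.

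**What to change.** In SAP 4.6.1, before unblinding:

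1. Present by product only AEs located at an identified patch cell, mapped to product through the randomization list (Listing 16.1.7.1). The sequence differs between induction and challenge, so the mapping must use the phase of the affected site.
2. State how an AE spanning several cells is counted.
3. Present all other AEs in the overall column only.
4. Restore the protocol's site-related/non-site-related split in Tables 14.3.1.2 and 14.3.1.4.
5. Confirm that the eCRF AE page captures the cell, and add the field if it does not. Recording the cell position rather than the product keeps the assessors blinded.
6. Enter the departure from the by-treatment-group display of protocol 12.2.7 in Table 5-1. If the Skin/Non-Skin split is kept instead of step 4, list that change there too.

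The cost is SAP and table-shell edits and possibly one eCRF field. No extra subjects, visits or procedures are needed.

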4.7 Analysis of Other Variables

N/A

5 Changes to the Protocol Defined Statistical Analysis Plan

Any changes from the originally planned statistical analysis specified in the protocol are outlined in [Table 5-1](#).

Table 5-1 Changes to Protocol Defined Analysis Plan

Protocol	Reporting & Analysis Plan	
Statistical Analysis section	Statistical Analysis Plan	Rationale for Changes

 6.8 Current and Concomitant Medication/Treatments(s): Medication or treatments taken within 30 days of signing the informed consent form will be documented as a prior medication/treatment. Medications or treatments taken after signing the informed consent, will be documented as concomitant medication/treatments. 	
 4.3.2 Prior and Concomitant Medications: Prior medications are defined as those which stopped before the start date of first study product administration in the study (i.e. in the induction phase). If the stop date is unknown or incomplete and the medication cannot be considered as stopped prior to the start date of first study product administration in the study (i.e. in the induction phase), then the medication will be considered as concomitant medication. ... Concomitant medications are defined as medications that are ongoing or started on or after the start date of first study product administration in the study (i.e. in the induction phase). 	
 Definition of Prior and Concomitant Medications was updated in order to keep consistent across other GSK CH studies.

 12.2.5 Primary Analysis(es): The number and percentage of subjects with any potential sensitization reactions versus those without any potential sensitization reactions will be presented by visit and treatment group. 	
 4.4.1.1 Primary Endpoint Definition The number and percentage of subjects with any potential sensitization reactions versus those without any potential sensitization reactions will be presented by product group. 	
 Potential Sensitization Reactions assessment performed by a blinded dermatologist will occur at final visit (i.e. Visit 15/Day 40), as defined in Section 4.1 of the Protocol.

Developmental cosmetic facial serum, lotion, and cream

212383

Final Version 1.0 Statistical Reporting and Analysis plan, 16 Jul 2019

Protocol	Reporting & Analysis Plan	
Statistical Analysis section	Statistical Analysis Plan	Rationale for Changes
		Because of this, the proportion of subjects with any potential sensitization reactions cannot be presented by visit, but only by product group.

Attachment 1: List of Data Displays

GSKCH_212383_TFL
List_FinalV1.0_16Jul20'
